10.1.3.2. Fluid retention replacement analysis

As fluid retention may possibly influence the weight increase, a sensitivity analysis will be performed for the primary endpoint "Mean change in body weight from baseline over 12 weeks", by considering as missing the values obtained in presence of fluid retention (for the definition of fluid retention, see Section 8.8 "Definitions").

Those missing values will be therefore imputed on the basis of the following rules for imputation:

- In case of one or more body weight assessments measured in presence of fluid retention, comprised between two assessments (pre- and post-) measured in absence of fluid retention, the lower value between the assessed weight(s) and the weight(s) estimated by the linear interpolation between pre- and postassessments will be imputed.
- If no subsequent values observed in absence of fluid retention are available, the post-baseline weight(s) recorded in presence of fluid retention will be imputed with the baseline value if that value is lower than the recorded value. Otherwise the recorded value will be used
- If fluid retention is already present at baseline (due to protocol violation), no imputation will be performed and observed values will be analyzed.

After imputation of these values, the imputation rule for the non-intermittent missing values described in Appendix 12.1 will be applied.

Furthermore, an additional sensitivity analysis will be performed for the primary endpoint "Mean change in body weight from baseline over 12 weeks", by excluding the patients for which fluid retention was reported at any time during the study.

HELSINN

T AN001 Effective Date 25 JUL 2022 Approved Version 2.00

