12.1.1.2. Imputation rules for Non-intermittent missing values (monotonic missingness)

Imputation rules for non-intermittent missing values are based on a main rule and some exceptions.

The rule and the exceptions will be applied separately for each efficacy parameter.

Main rule

All missing values will be imputed assuming MNAR, specifically by means of the control-based multiple imputation method.

Reason: Most of the patients are expected to have missing values from time of treatment stop. In addition, the patients under study are characterized by poor prognosis and the reasons for treatment discontinuation are expected to be more related to the background disease than to treatment failure. For this reason, it cannot be assumed that the values after the treatment discontinuation would follow the same trend as before discontinuation because the general conditions, with specific exceptions described below, after discontinuation get to worsen. The implementation of the control-based imputation is conservative because it assumes that the deterioration of the patient condition affects mainly the patients in the active treatment group.

Exceptions

- 1. Independent from reason for discontinuation of treatment, if:
 - at least two non-missing post-baseline assessments are available (first assessment = X_1 and last assessment = X_{last}) and,
 - X_{last} $X_1 \ge 0$ and $X_{\text{last}} \ge$ baseline,

then impute all the missing values with the MAR multiple imputation approach including randomised treatment as the covariate.

- 2. If reason for discontinuation of treatment = "Physician decision" or = "Withdrawal by subjects" and:
 - \circ at least two non-missing post-baseline assessments are available (first assessment = X1 and last assessment = X_{last}) and,
 - $\circ \quad X_{\text{last}} \text{ } X_1 \text{ < 0 and } X_{\text{last}} \text{ < baseline,}$

then impute all missing values to the worst value observed for the subject, considering only the on-treatment (post-baseline) timepoints.

Reasons:

Imputation for Exception 1

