This exception is applicable for any reason for discontinuation, when the trend reveals an improvement of the efficacy assessments over time, with the last post-baseline assessment (X_{last}) better than both the baseline and the first post-baseline assessment (X₁). Based on these conditions, it is assumed that the decision of stopping the treatment is not related to the treatment itself (since the efficacy parameter was improving over time). Due to the improvement over time, it can also be assumed that

the treatment effect would have been maintained as it was before interruption for the rest of the observation period. For this reason, the missing values after the treatment discontinuation will be imputed with the Missing at Random (MAR) multiple imputation approach including randomized treatment as the covariate. This approach might be slightly optimistic for values missing at visits far from the visit of the last assessment, however this will not impact the primary endpoint that is limited to week 12, considering that at least assessments at week 3 and at week 6 are requested by the rule.

Imputation for Exception 2

Business & Decision

Life Sciences

This exception is limited to the reasons of treatment discontinuation that are most likely related to lack of efficacy of the treatment; the criterion for considering the unknown values as related to lack of efficacy is the negative trend of the observed efficacy assessments over time, as documented by the last post-baseline assessment (X_{last}) worse than the baseline and the first post-baseline assessment (X_1). Based on these conditions, it is assumed that the decision of stopping the treatment can be related to the treatment itself (lack of efficacy). The missing values will be imputed with the worst value observed for the patient considering only the on-treatment (post-baseline) timepoints.

Final revision of the above rules was done at the BDRM and they have been confirmed.

The details of the process are showed in the following steps.

STEP 1: Single/Multiple imputations

- Impute all intermittent missing data
- Create 100 records for each value
- Application of the Main Rule:

Apply MNAR Control-Based imputation on all subjects (placebo and active treatment) with at least one missing assessment.

- MI on all non-intermittent missing

- only placebo patients contribute to the imputation.

Expectation after imputation: only 1 dataset including:

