- ANAM and placebo patients without missing data (all assessments observed)
- ANAM and placebo patients with at least 1 missing assessment imputed by the imputation process.

Note: it is theoretically possible that aberrant values are derived because of the imputation. Aberrant values are defined as follows:

- For each item of the questionnaires:
 - a) Imputed value < the lower limit (0)
 - b) Imputed value > the upper limit (4)
- \circ For the body weight:
 - a) Imputed value < the lower limit (30 Kg)
 - b) No upper limit for the Body Weight is fixed.

In the cases (a) the imputed value will be set equal to the lower value.

In the cases (b) the imputed value will be set equal to the upper value.

Unscheduled assessments of body weight and questionnaires are not considered for imputations. These values will be listed only (and have all ANL0XFLs set to blank).

 Application of Exception 1: Apply MAR (as correction to the previous control-based imputation on patients fulfilling Exception 1) *Note: Values to be imputed with MAR need first to be re-set at missing.* A flag before starting with the imputation process should identify the cases where the exception 1 should be applied. Imputed values after MAR imputation should be within the aberrant values described above for the MNAR imputation
 According to Exception 2: Impute worst value at subject level.

A flag before starting with the imputation process should identify the cases where the exception 2 should be applied. Worst value should be calculated before any imputation.

- The imputation process does not distinguish between missing due to treatment discontinuation and death. All imputed assessments after death must be set to missing.

No covariates, apart from treatment arm (as by variable or covariate, as relevant) and baseline value will be included in the MI models.

For each variable, 100 imputed values will replace each missing value.

The following variables will be separately imputed according to the above mentioned single or multiple imputation methods:

- Weight
- 5-IASS
- 4-item Anorexia Concerns Subscale (4-IACS)
- 12-item A/CS domain

Business & Decision

Life Sciences

- FAACT total score
- FACT-G total score
- FAACT TOI
- Functional Assessment of Chronic Illness Therapy-Fatigue (FACIT-F)
- FACIT-F TOI score

The PGIS and the PGIC endpoints and the hunger assessment will not be imputed.

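### In the fluid-retention sensitivity analysis, patients with no fluid-free weight gain can still meet Exception 1, so their missing visits are imputed under MAR with treatment in the model

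*SAP*

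**What the plan says.** SAP 10.1.3.2 treats weights measured in the presence of fluid retention as missing and replaces them by fixed rules. Where no later fluid-free weight exists, a post-baseline weight "recorded in presence of fluid retention will be imputed with the baseline value if that value is lower than the recorded value"; otherwise the recorded weight stays. The order of steps is then given: "After imputation of these values, the imputation rule for the non-intermittent missing values described in Appendix 12.1 will be applied".

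Under SAP 12.1.1.2 the main rule for trailing missing values is control-based imputation, to which only placebo patients contribute. Exception 1 overrides it, whatever the reason for discontinuation, when "at least two non-missing post-baseline assessments are available", the last is not below the first, and the last is not below baseline. The instruction is "then impute all the missing values with the MAR multiple imputation approach including randomised treatment as the covariate". The stated reason is that the weights were improving, with the last one above both baseline and the first post-baseline weight, so that "the treatment effect would have been maintained as it was before interruption for the rest of the observation period".

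On timing, 12.1.1.2 says: "A flag before starting with the imputation process should identify the cases where the exception 1 should be applied". Neither section says whether, in the fluid-retention analysis, this comes before or after the oedema replacement. By contrast, the COVID-19 analysis (SAP 10.1.3.3) does state how Exception 1 applies to home-collected weights set to missing.

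**The concern.** The analysis exists to show that fluid does not explain the weight effect. For a patient whose only gain was fluid, it should remove the gain and also any inference drawn from it. The reset does the first. It does not reliably do the second, because a weight set equal to baseline satisfies a rule written with weak inequalities. The patient is then handled as someone who was improving, when the fluid-free record shows no improvement. Fluid can therefore still decide the imputation route in the one analysis meant to take fluid out, and the check is somewhat weaker than it appears.

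**Working it through.** The plan gives no figure for this point, so the check is one of rule logic, followed by an illustrative size.

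**Inputs from the documents.** The reset rule and order of steps (SAP 10.1.3.2); Exception 1 and the flag (12.1.1.2); imputation models containing only treatment, baseline and earlier visits (12.1.1.2 and the code in 12.2.1.2); an effect of about 1.8 kg (7.2); 318 patients randomised 1:1 (4.1), so about 159 per arm. Visit profiles, correlations, SDs and patient counts below are assumptions.

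**Step 1: logic.** Let B be baseline and R a trailing oedema weight. The replaced value is min(R, B). Exception 1 needs at least two values, X_last − X_1 ≥ 0 and X_last ≥ B. If the last weight is reset, X_last = B. The third condition becomes B ≥ B, which is always true, and the second becomes X_1 ≤ B. That holds when X_1 was itself reset, or was at or below baseline.

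**Step 2: examples.** Baseline 50 kg, two post-baseline weights, then later visits missing with the patient alive.

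| Recorded weights | Exception 1 on recorded weights | After replacement | On fluid-free weights only |
|---|---|---|---|
| 53 oedema, 54 oedema | 54 − 53 = 1: met | 50, 50; difference 0: met | no weights: not met |
| 49 dry, 53 oedema | 53 − 49 = 4: met | 49, 50; difference 1: met | one weight: not met |
| 53 oedema, 51 oedema | 51 − 53 = −2: not met | 50, 50; difference 0: met | no weights: not met |
| 51 dry, 53 oedema | 53 − 51 = 2: met | 51, 50; difference −1: not met | one weight: not met |

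With a single post-baseline weight the exception is never met.

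**Step 3: enumeration.** Recorded changes from baseline of −3, −1, 0, 1 or 3 kg were crossed with oedema present or absent at each visit, with the last visit in oedema and above baseline. Among patterns with no fluid-free weight above baseline, Exception 1 is met as follows.

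| When the flag is set | Two visits | Three visits |
|---|---|---|
| After replacement | 16/16 | 128/128 |
| On recorded weights | 15/16 | 120/128 |
| On fluid-free weights only | 0/16 | 6/128 |

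So the reset newly creates the status in 16 − 15 = 1 and 128 − 120 = 8 patterns. In the rest it leaves in place a status that the oedema weights already gave. These are counts of patterns, not expected numbers of patients.

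**Step 4: size in one anamorelin patient** reset to baseline at Weeks 3 and 6 and missing Weeks 9 and 12. The MAR model adds only the treatment effect that remains after conditioning on earlier weights. Assume effects e of 1.2, 1.8, 2.1 and 2.2 kg at Weeks 3, 6, 9 and 12 (mean 7.3/4 ≈ 1.8), a regression ρ on the previous visit, and a mean over four visits:

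- d9 = 2.1 − 1.8ρ
- d12 = (2.2 − 2.1ρ) + ρ·d9
- added to the 12-week mean: (d9 + d12)/4

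ρ = 0.95: (0.39 + 0.58)/4 ≈ 0.24 kg. ρ = 0.85: (0.57 + 0.90)/4 ≈ 0.37 kg. ρ = 0.70: (0.84 + 1.32)/4 ≈ 0.54 kg.

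A simulation refitting both regressions on baseline and all earlier visits used random-walk weights (step SD 1.5 kg) and added measurement error of 0 or 1.0 kg. MAR minus control-based was 0.00 to 0.05 kg for a constant 1.8 kg effect, 0.00 to 0.09 kg for a plateau (1.5, then 1.9 kg), and 0.53 to 0.65 kg for linear growth (0.72 to 2.88 kg).

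**Step 5: arm level.** If ten anamorelin patients were affected (an assumption), the arm mean would shift by at most 0.65 × 10/159 ≈ 0.041 kg, about 2% of 1.8 kg (0.041/1.8 = 0.023). The four-visit formula in Step 4 gives 0.24 × 10/159 ≈ 0.015 to 0.54 × 10/159 ≈ 0.034 kg.

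**The case against.** The other side has five arguments.

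1. A reader might infer that the reset makes patients meet Exception 1 by construction. The rules do not support that. Only the comparison with baseline is automatic. Most patterns without fluid-free gain already qualified on the recorded weights, and a patient with an early dry gain followed by a reset moves to control-based imputation, the conservative direction. This stands, and the point is limited accordingly.

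2. The problem does not arise on every reading. SAP 12.1 says fluid-affected weights are first set to missing and then imputed, Exception 1 counts non-missing weights, and the flag precedes imputation. A flag set after blanking and before replacement would use fluid-free weights only. The text allows this reading, but the order stated in 10.1.3.2 does not favour it, and the outcome should not depend on the programmer's choice.

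3. The analysis still removes most of the fluid gain. For the 53/54 patient, MAR from 50/50 instead of 53/54 lowers the 12-week mean by (3 + 4 + 4ρ + 4ρ²)/4, which is 3.6 kg at ρ = 0.95 and 2.9 kg at ρ = 0.70. Against that, 0.24 to 0.54 kg is in dispute. This stands.

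4. Companion analyses exist. SAP 10.1.3.1 drops the exceptions, and 10.1.3.2 also excludes every patient with fluid retention at any time. They help, but the first keeps the oedema weights as recorded and the second selects on a post-randomisation event. Neither combines oedema replacement with control-based imputation.

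5. Few patients may be affected. SAP section 13 dropped the fluid-retention subgroup for inadequate numbers, and oedema was an exclusion criterion re-checked at Visit 2. This points to a small effect but gives no count.

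**Conclusion.** The point holds in limited form. On the plain order of steps in 10.1.3.2, a patient with at least two post-baseline weights, no fluid-free gain, a trailing weight reset to baseline and later visits missing meets or keeps Exception 1. That patient is imputed under MAR with treatment in the model, contrary to the SAP's own rationale of an observed improvement. Flagging on recorded weights usually gives the same result.

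The likely size is about 0 to 0.65 kg on an affected patient's 12-week mean, near zero if the drug effect is early or plateaus and larger if it keeps growing. At arm level it is a few hundredths of a kilogram or less for ten assumed patients. All of this rests on assumed profiles and an unknown patient count.

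A reader might infer that the whole 1.8 kg effect is put back, or that the primary result is in doubt. Neither follows: the MAR model conditions on the reset weights, and the primary analysis uses neither the reset nor this sequence. Only visits missing at Week 9 or Week 12 bear on the 12-week endpoint.

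**What to change.** Add to SAP 10.1.3.2: a patient with any trailing weight reset to baseline qualifies for Exception 1 only if its conditions also hold on at least two post-baseline weights measured without fluid retention; otherwise the main control-based rule applies. State that the Exception 1 flag in this analysis is set on that basis. Leave Exception 2 unchanged, because moving declining patients from their worst observed value to the main rule could make their imputed weights more favourable.

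The cost is one sentence and one flag in a sensitivity analysis. The estimate may become slightly less favourable. The rule also moves some patients with a single dry weight above baseline to the main rule: in the three-visit enumeration, 12 of the 72 patterns with some fluid-free gain. If the analysis has already been run, report this as an additional sensitivity result, labelled as such, with the number of patients whose imputation route changes in each arm.

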10.1.3.3. COVID-19 sensitivity analysis

Business & Decision

Life Sciences

In case the subject was unwilling or unable to reach the research site or the site was not able to accommodate the visits during the COVID-19 pandemic, body weight was collected by the subject at home. Despite the recommendations to make the body weight data collection as most uniform as possible (8), high heterogeneity can be expected. This might possibly have an impact on the overall results.

A sensitivity analysis will be performed for the primary endpoint "Mean change in body weight from baseline over 12 weeks", by considering as missing the body weight values obtained when collected at home by the subject.

Those missing values will be therefore imputed on the basis of the following rules for imputation:

- In case of one or more intermittent missing value comprised between two assessments (pre- and post-) measured at site, the weight value(s) estimated by the linear interpolation between pre- and post-assessments will be imputed.
- In case of no intermittent missingness (the weight values set at missing because collected at home during COVID-19 pandemic are the last ones and no other "post" assessment is performed at site) the imputation rule for the non-intermittent missing values described in Appendix 12.1.1.2 will be applied with the following update:
 - All missing values (including also the weight values set at missing because collected at home) will be imputed assuming MNAR, specifically by means of the control-based multiple imputation method.
 - The exception 1, imputation of the missing values with the MAR approach under the circumstances described in Appendix 12.1.1.2, will be applied also on the subset of patients set at missing because collected at home

10.1.3.4. *Mis-stratification sensitivity analysis*

During the course of the study and as part of the data and medical review process, some cases of mis-stratifications (i.e.: incorrect stratification information entered into the IRT system for the purpose of the randomization of the patients) were observed and investigated with the sites involved. The final list of mis-stratifications, confirmed by the PIs, was reviewed and discussed during the BDRM.

Since the percentage of patients affected by such procedural deviations was about 7,5%, even if any imbalance due to such randomization errors is expected to be minimal, a sensitivity analysis will be performed for the co-primary endpoint on the ITT set, using the correct strata information as part of the covariates included in the statistical model. Specifically, for the 5-item Anorexia Symptom Subscale stratum (≤ 10 vs >10), the correct information is available in the clinical database (as part of the baseline assessments), while for the other two strata (systemic anti-cancer treatment line and cancer treatment), not being part of the clinical database variables, the correct

HELSINN

information to be incorporated into ADaM, displayed in the listings and used for the sensitivity analysis will be provided as external data, according to sites confirmation (see BDRM minutes and related attachment).

10.1.4. Supportive analyses

10.1.4.1. Analyses on the FAS.

Similarly to the primary efficacy analysis in the ITT set, the analyses will be conducted on the FAS set.

10.1.4.2. Analysis on the PP set

Similarly to the primary efficacy analyses, the analyses will be conducted on the PP set.

10.1.4.3. Analysis on subgroups of the co-primary endpoint

Similarly to the primary efficacy analyses, analyses will be conducted on the ITT Set based on the subgroups defined in Section 8.6. The statistical analyses and models will be based on the models used for the co-primary endpoints described in Section 10.1.2.

A forest plot presenting point estimates and 95% confidence intervals will be presented for weight and 5-IASS.

10.1.4.4. *Premature discontinuation and retrieved dropouts*

In order to summarize the presence of retrieved dropouts in the data of body weight and 5-IASS, a frequencies for patients who have the last efficacy assessment at the same week as the last treatment given as well as retrieved dropouts patients will be calculated. The number and percentage of patients will be presented for each category, including a sub-category of patients who have the last efficacy assessment at the same week as the last treatment given and who stayed alive during the study. Summaries will be done separately for body weight and for 5-IASS by treatment arm on the ITT set.

10.2. Secondary Efficacy Endpoints

All the analyses of the secondary endpoints will be conducted on the ITT set.

The following secondary endpoints are to be analyzed:

- Duration of treatment benefit in body weight (≥0 kg) over 12 weeks
- Duration of treatment benefit in body weight (≥ 1.5 kg) over 12 weeks
- Duration of treatment benefit in 5-item Anorexia Symptom Subscale (≥0 points) over 12 weeks

- Duration of treatment benefit in 5-item Anorexia Symptom Subscale (≥ 3 points improvement) over 12 weeks
- Mean change in FAACT 12-item A/CS domain score from baseline over 12 weeks
- Mean change in FACIT-F from baseline over 12 weeks

Life Sciences

• Mean change in FAACT total score from baseline over 12 weeks

As described in Section 7.3 the secondary efficacy endpoints analyses will be performed by following a hierarchical order.

Subgroup analysis for the secondary endpoints, are defined in Section 8.6.

10.2.1. Secondary efficacy endpoints derivation Secondary endpoints based on Duration of treatment benefit

The duration of treatment benefit over 12 weeks is not directly collected in the study data but should be derived from:

- the dates of the assessments (either observed or imputed),
- the values of the assessments (either observed or imputed)

The duration of treatment benefit over 12 weeks is measured as the period, or the sum of the periods, over 12 weeks (or less in case of death), in which the patient observed a change from baseline superior or equal to the threshold.

For the purpose of computation, it will be assumed a linear evolution between two measurements.

Below some examples (threshold = 0. Same approach in case of threshold=clinical meaningfulness)

T AN001 Effective Date 25 JUL 2022 Approved Version 2.00

Case 1: benefit all over 12 weeks. No need of linear interpolation

Duration of treatment benefit = Date of Week 12 – Date of Baseline assessment Case 2: benefit until a given visit. Need of linear interpolation

The equation of the line passing through two given points: (x1, y1) and (x2, y2) is the following:

(Y - Y1)/(Y2 - Y1) = (X - X1) / (X2 - X1)

Where Y=0 if the threshold=0 (or =clinical meaningfulness threshold, otherwise) and:

X1=date of the Visit at Week 9

HELSINN

T AN001 Effective Date 25 JUL 2022 Approved Version 2.00

Y1=value of assessment (e.g., Body Weight) at Week 9

X2=date of the Visit at Week 12

Business & Decision

Life Sciences

Y1=value of assessment (e.g., Body Weight) at Week 12

Setting Y=0 (threshold value), the equation estimates the time X_T when the benefit ends.

The duration of benefit will be = (Date of Week 9 – Date of Baseline assessment) + (Date of X_T – Date of Week 9).

These examples describe cases with all assessments available (e.g.; after multiple imputation).

The same approach will be applied to derive the endpoints before the multiple imputation (observed values, to be presented as descriptive statistics).

If treatment benefit is not reached, the duration of treatment benefit in this patient will be set to 0; these patients will be included into the statistical analysis.

Secondary endpoints based on Mean Change from baseline over 12 weeks

The mean change effect for these secondary endpoints will be computed as sum of the changes from baseline over 12 weeks by the time of the last assessment (either week 12 or before), and then divided by the number of assessments (observed or imputed) from baseline up to the time of the last assessment (either week 12 or before, in case of death). This is aligned to the approach followed for the main analysis of the co-primary endpoints.

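### SAP 10.2.1: the Case 2 formula for duration of benefit contradicts its own definition, by using raw values throughout and, at the 1.5 kg and 3-point thresholds, by counting time before benefit starts

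*SAP*

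**What the plan says.** SAP 10.2.1 defines the duration of treatment benefit as the period, or the sum of periods, over 12 weeks "in which the patient observed a change from baseline superior or equal to the threshold". For the computation, "it will be assumed a linear evolution between two measurements". Protocol 9.4.5.3 gives the same definition. SAP 8.8 defines change from baseline as the visit value minus the baseline value.

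Examples follow. They are introduced for threshold 0, with the note "Same approach in case of threshold=clinical meaningfulness". Case 1 (benefit throughout) takes Week 12 date minus baseline date. Case 2 (benefit until some visit) uses the line through two points:

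- The target ordinate: "Where Y=0 if the threshold=0 (or =clinical meaningfulness threshold, otherwise) and".
- The first ordinate: "Y1=value of assessment (e.g., Body Weight) at Week 9".
- The second ordinate: "Y1=value of assessment (e.g., Body Weight) at Week 12". The label Y1 is repeated, so Y2, which the equation needs, is never defined.
- The solution: "the equation estimates the time X_T when the benefit ends".
- The sum: "The duration of benefit will be = (Date of Week 9 – Date of Baseline assessment"), plus the time from Week 9 to X_T.

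The thresholds above zero are 1.5 kg and 3 points (SAP 6.1.2 and 8.8).

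**The concern.** Two features of Case 2 do not fit the definition above it.

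1. **Scale.** Y is a threshold for change, but both ordinates are assessed values. The equation therefore asks when body weight itself reaches 0 or 1.5 kg, or when the 5-IASS score itself reaches 0 or 3.
2. **Start of the count at positive thresholds.** Case 2 dates only the end of benefit and counts from the baseline assessment. Change at baseline is 0, so at 1.5 kg or 3 points nobody is in benefit on that date. The printed sum then includes time before the threshold is first reached.

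Duration endpoints hold the first four of the seven secondary places in the sequential hierarchy (SAP 7.3). The two with positive thresholds are second and fourth, so their results decide whether later endpoints are tested.

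The two errors differ in visibility. A raw-value error mostly gives impossible dates. Extra time before onset gives durations inside 84 days that look ordinary. Patients who never reach benefit are set to 0, so the extra days would go only to patients who reach the threshold, by amounts that depend on how fast they reach it.

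**Working it through.** **Inputs.** The SAP 4.1 schedule has baseline on Day 1 and later visits on Days 22, 43, 64 and 85, so elapsed days are 21, 42, 63 and 84. Thresholds are 0, 1.5 kg and 3 points. The patient values are illustrative assumptions. The plan prints no numerical result for Case 2, so there is no figure to reproduce.

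**Formula.** Solving the SAP's line for X, and reading the Week 12 label as Y2:

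X_T = X1 + (Y − Y1)/(Y2 − Y1) × (X2 − X1), with X1 = 63 and X2 = 84.

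**Step 1: raw values against change.**

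| Patient (baseline; Week 9; Week 12) | Threshold | Raw values | Change from baseline |
|---|---|---|---|
| Weight 50; 52; 49 kg | 0 | 63 + (0−52)/(49−52)×21 = 427 | 63 + (0−2)/(−1−2)×21 = 77 |
| Same | 1.5 kg | 63 + (1.5−52)/(49−52)×21 = 416.5 | 63 + (1.5−2)/(−1−2)×21 = 66.5 |
| 5-IASS 8; 12; 8 | 3 | 63 + (3−12)/(8−12)×21 = 110.25 | 63 + (3−4)/(0−4)×21 = 68.25 |
| 5-IASS 6; 10; 2 | 3 | 63 + (3−10)/(2−10)×21 = 81.375 | 63 + (3−4)/(−4−4)×21 = 65.625 |

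The first three raw dates lie beyond day 84. The last lies inside the visit bracket and is 81.375 − 65.625 = 15.75 days late. That pattern is unusual. The score must be at least baseline + 3 at Week 9 and below 3 at Week 12, which is a fall larger than the baseline score in three weeks.

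**Step 2: counting from baseline at threshold 0.** The Case 2 sum is (63 − 0) + (X_T − 63) = X_T. For weights 50, 51, 51.5, 51, 49 kg the changes are 0, +1, +1.5, +1, −1, so X_T = 63 + (0−1)/(−1−1)×21 = 73.5. The definition also gives 73.5, because a change of 0 at baseline meets the criterion. There is no conflict.

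**Step 3: counting from baseline at positive thresholds, with change already used.**

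- Weight +3, +3, +3, 0 kg, threshold 1.5 kg. End: 63 + (1.5−3)/(0−3)×21 = 73.5. Start: 21×1.5/3 = 10.5. Definition: 73.5 − 10.5 = 63.0. Case 2: 73.5, which is 10.5 days too many.
- Same patient with Week 3 change 0. Start: 21 + 21×1.5/3 = 31.5. Definition: 73.5 − 31.5 = 42.0. Case 2: 73.5, which is 31.5 days too many.
- 5-IASS +4, +4, +4, 0, threshold 3. End: 63 + (3−4)/(0−4)×21 = 68.25. Start: 21×3/4 = 15.75. Definition: 68.25 − 15.75 = 52.5. Case 2: 68.25, which is 15.75 days too many.

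When the threshold is reached by Week 3, the excess is 21 × threshold / (Week 3 change). It is 21 days if the threshold is just met and 10.5 days at twice the threshold.

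**Step 4: Case 1 at a positive threshold.** With +2 kg at every visit and threshold 1.5 kg, the start is 21×1.5/2 = 15.75 and the definition gives 84 − 15.75 = 68.25 days. Case 1 gives 84.

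**The case against.** The best defence is that the rule printed above the examples is correct and governs. It is on the change scale, allows several periods and specifies linear interpolation. Setting Y = 0 for body weight makes sense only for changes, and the SAP floors imputed weights at 30 kg (12.1.1.2), so the raw reading is unworkable and points to a drafting slip. The note extending the examples can be read as meaning only that interpolation is done at the threshold, and the line equation dates an upward crossing as readily as a downward one. SAP 12.4 lets the QC statistician use code review or hand calculation and requires a check for spurious values. Consistency with the SAP includes consistency with its definition. Graphs may also have accompanied the cases. None is visible, so the point rests on the printed text.

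Much of this stands. A programmer who follows the definition gets the right durations, and the raw-value error would usually be found. What does not stand is the view that positive thresholds merely lack an example. Case 2 itself puts the clinically meaningful threshold into Y, solves only for the end of benefit, and starts its sum at baseline. Someone coding from that formula gets a plausible wrong number, and a checker would find one part of the SAP supporting it.

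**Conclusion.** The printed Case 2 formula conflicts with the definition it is meant to illustrate. The raw-value wording and repeated Y1 apply at every threshold, with a large but mostly visible effect. The count from baseline conflicts with the definition only at 1.5 kg and 3 points, where Case 1 has the same defect. The excess in the illustrations is 10.5 to 31.5 days out of 84. These sizes depend on the assumed patients and on nominal visit days.

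Three stronger readings might be inferred, and the documents support none of them:

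- That counting from the baseline date is wrong in general. At threshold 0 it is what the definition requires in the worked example.
- That a wrong computation is planned. The general definition is right, so an error is possible but not shown to be intended.
- That the secondary results would be biased in favour of one arm. No size or direction of between-arm bias is shown.

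The co-primary endpoints do not use this derivation. Severity is minor to should-fix. This corrects a formula that contradicts its own definition and does not dispute the choice of endpoint or analysis.

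**What to change.** In SAP 10.2.1:

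1. Define Y1 and Y2 as change from baseline at the earlier and later of two consecutive visits, and correct the second Y1 to Y2.
2. State that, at every threshold, the same equation dates each upward and each downward crossing, and that duration is the sum of (end minus start) over all benefit periods. Threshold 0 needs this too, for a patient who falls below baseline and recovers.
3. State that the baseline date is a start only when the threshold is 0.
4. Keep actual assessment days, as in SAP 8.7.

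The cost is a few words. The endpoint definition, the data and the testing order do not change. The change is best made before unblinding. The documents do not say whether unblinding has taken place, so the correction should be dated and recorded as bringing the formula into line with the existing definition.
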